9.4. Statistical Analyses

9.4.1. General Statistical Considerations

Statistical analysis of this study will be the responsibility of Lilly or its designee. The analyses for this study will be descriptive, except for possible exploratory analysis as deemed appropriate. Data analyses will be provided by study part, dose group, and for all study patients combined wherever appropriate. For continuous variables, summary statistics will include number of patients, mean, median, standard deviation, minimum, and maximum. Categorical variables will be summarized using number of patients, frequency, and percentages. Missing data will not be imputed, except for missing date of birth for analysis purpose. If birth year and month is available and date is not available or missing, date will be imputed to the 15th of that month. Refer to the statistical analysis plan for this study for further detail.

The interpretation of the study results will be the responsibility of the investigator with the Lilly CRP/CRS, pharmacokineticist, and statistician. The Lilly CRP/CRS and statistician will also be responsible for the appropriate conduct of an internal review for both the final study report and any study-related material to be authorized by Lilly for publication.

Any change to the data analysis methods described in the protocol will require an amendment ONLY if it changes a principal feature of the protocol. Any other change to the data analysis methods described in the protocol, and the justification for making the change, will be described in the CSR. Additional exploratory analyses of the data will be conducted as deemed appropriate.

9.4.2. Analysis Population

All entered patients will be used in summarizing patient disposition. All treated patients (safety population) will be used in analyzing patient characteristics and safety and efficacy data.

9.4.3. Participant Disposition

A detailed description of participant disposition will be provided. It will include a summary of the number and percentage of patients entering the study, treated, reasons for discontinuation from study treatment, and reasons for discontinuation from study. Reasons of discontinuation from study treatment and study will be listed.

All clinically relevant protocol deviations will be listed by pre-determined categories (e.g. inclusion/exclusion criteria, non-compliance with protocol procedures, drug dosage/intervention, use of excluded treatments, informed consent/assent process, continuing after meeting withdrawal criteria, or other).

9.4.4. Patient Characteristics

Patient characteristics will include a summary of the following:

- Patient demographics
- Baseline disease characteristics
- Prior disease-related therapies
- Concomitant medications

Other patient characteristics will be summarized as deemed appropriate.

9.4.5. Safety Analyses

All patients who have received at least 1 dose of any study treatment will be evaluated for safety and toxicity.

Safety analyses will include summaries of the following:

- Adverse events, including severity and possible relationship to study drug
- Dose adjustments
- Vital signs
- Dose-limiting toxicities
- Laboratory values

9.4.6. Efficacy Analyses

The study was not designed to make an efficacy assessment in Parts A and B, CCI

The following efficacy measures will be listed and summarized where appropriate.

9.4.6.1. Parts A and B Efficacy Analyses

Parts A and B will not have a formal efficacy assessment. The following efficacy measures are important secondary endpoints measured using RECIST v1.1 or RANO criteria.

Objective Response Rate (ORR): The ORR is the percentage of patients with a best response of complete response [CR] or partial response [PR].

Duration of Response (DoR): The DoR is defined only for responders (patients with a CR or PR). It is measured from the date of first evidence of a CR or PR to the date of objective progression or the date of death due to any cause, whichever is earlier.

Disease Control Rate (DCR): The DCR is the percentage of patients with a best response of CR, PR, or stable disease (SD).

Clinical Benefit Rate (CBR): The CBR is the percentage of patients with a best response of CR or PR, or SD for at least 6 months.

Progression-free survival (PFS): Progression-free survival is measured as the time from first dose of any study drug to progressive disease or death, whichever occurs first. The PFS rate will be calculated at appropriate time intervals (e.g. at 3 and 6 months).

9.4.6.2. Part C Efficacy Analyses

In Part C, the primary efficacy measure is investigator-assessed tumor response as defined by INRC. The primary endpoint ORR will be based on the 2017 INRC (Park et al. 2017) as described in Section 9.4.6.2.1. The primary analysis of ORR will occur 6 cycles after last patient has entered treatment, in order to ensure adequate response and durability of response data is available at the time of analysis. The point estimate of ORR with a two-side exact 95% confidence interval will be provided, and one-sided exact p-value will be reported.

9.4.6.2.1. 2017 INRC

For Part C, efficacy will be evaluated using the 2017 INRC (Park et al. 2017).

A responder is defined as any patient who exhibits a CR, PR, or MR.

The response criteria integrate the response of all lesions using CT/MRI and/or MIBG/FDG-PET lesions, and assessment of bone marrow disease.

Primary tumor (soft tissue) response is as follows:

- **Complete Response (CR):**
 - <10 mm residual soft tissue at primary site AND
 - complete resolution of MIBG-avid tumors or FDG-PET uptake (for MIBG-nonavid tumors) at primary site
- **Partial Response (PR):**
 - ≥30% decrease in longest diameter of primary site AND
 - MIBG-avid tumors or FDG-PET uptake (for MIBG-nonavid tumors) at primary site is stable, improved, or resolved
- **Stable Disease (SD):** Neither PR nor PD at the primary site
- **Progressive Disease (PD):**
 - >20% increase in longest diameter taking as reference the smallest sum while on study, including baseline sum if that is the smallest, AND
 - minimum absolute increase of 5mm in longest dimension
 - Note: a lesion that does not meet PD measurement criteria but has fluctuating MIBG avidity will not be considered PD

Soft tissue and bone metastatic disease tumor response is as follows:

- **Complete Response (CR):** Complete resolution of all disease sites defined as:
 - nonprimary target and nontarget lesions <10 mm AND
 - lymph nodes identified as target lesions decrease to a short axis <10 mm AND
 - MIBG-avid update or FDG-PET uptake (for MIBG-nonavid tumors) of nonprimary lesions resolves completely
- **Partial Response (PR):** ≥30% decrease in sum of diameters^a of nonprimary target lesions compared with baseline AND all of the following:

- Nontarget lesions may be stable or smaller in size AND
- $\geq 50\%$ reduction in MIBG absolute bone score (relative MIBG bone score ≥ 0.1 to ≤ 0.5) or $\geq 50\%$ reduction in number of FDG-PET-avid bone lesions^{b,c} AND
- No new lesions
- **Progressive Disease (PD)**: Any of the following:
 - Any new soft tissue lesion detected by CT/MRI that is also MIBG avid or FDG-PET avid
 - Any new soft tissue lesion seen on anatomic imaging that is biopsied and confirmed to be neuroblastoma or ganglioneuroblastoma
 - Any new bone site that is MIBG-avid
 - A new bone site that is FDG-PET avid (for MIBG-nonavid tumors) AND has CT/MRI findings consistent with tumor OR has been confirmed histologically to be neuroblastoma or ganglioneuroblastoma
 - $>20\%$ increase in longest diameter taking as reference the smallest sum on study (this includes the baseline sum if that is the smallest on study) AND minimum absolute increase of 5 mm in sum of diameters of target soft tissue lesions
 - Relative MIBG score $\geq 1.2^c$
- **Stable disease (SD)**: Neither PR nor PD of nonprimary lesions

^a Sum of diameters is defined as the sum of the short axis of discrete lymph nodes (ie, cervical, axillary nodes) added to the sum of the longest diameters of non-lymph node soft tissue metastases. Masses of conglomerate nondiscrete lymph nodes will be measured using longest diameter.

^b For patients with soft tissue metastatic disease, resolution of MIBG and/or FDG-PET uptake at the soft tissue sites is not required; all size reduction criteria must be fulfilled.

^c MIBG scoring of bone lesions will consist of 9 sectors (cranio-facial, cervical and thoracic spine, ribs/sternum/clavicles/scapula, lumbar and sacral spine, pelvis, upper arms, lower arms and hands, femurs, and lower legs and feet). Each sector will be scored from 0-3 (0=no sites; 1=1 site; 2= more than 1 site; 3=massive involvement [$>50\%$ of segment]) using the Curie scoring method (maximum absolute score of 27). The score of each sector will be collected in the CRF. Relative MIBG score is the absolute score for bone lesions at time of response assessment divided by the absolute score for bone lesions at baseline before therapeutic interventions. The same scoring method (eg, Curie) must be used at all assessment time points. MIBG single-photon emission computed tomography (SPECT) or MIBG-SPECT/CT may be used for scoring purposes, but the same imaging methodology should be used for all evaluations.

Bone marrow response is determined by cytology (recommended to be accompanied by immunocytoLOGY)/histology (accompanied by immunohistochemistry [Burchill et al. 2017]). Use the bone marrow sample with the highest percentage of tumor infiltration to assess response.

Grading is as follows:

- **Complete Marrow Response**: No tumor infiltration on reassessment, independent of baseline tumor involvement
- **Progressive Marrow Disease**: either
 - bone marrow without tumor infiltration that becomes $> 5\%$ tumor infiltration on reassessment, or

- bone marrow with tumor infiltration that increases by >2 times and has >20% tumor infiltration on reassessment
- **Minimal Disease (MD):** any of the following:
 - $\leq 5\%$ tumor infiltration at baseline and remains > 0 to $\leq 5\%$ tumor infiltration on reassessment, or
 - no tumor infiltration at baseline and $\leq 5\%$ tumor infiltration on reassessment, or
 - $> 20\%$ tumor infiltration at baseline and > 0 to $\leq 5\%$ tumor infiltration on reassessment
- **Stable Marrow Disease:** Persistence of $> 5\%$ tumor infiltration on reassessment that does not meet the criteria for CR, MD, or PD.

Overall response is as follows:

- **Complete Response (CR):** All components meet criteria for CR
- **Partial Response (PR):**
 - PR in ≥ 1 component AND
 - ALL other components are either CR, MD (bone marrow only), PR (soft tissue or bone), or NI (site not involved at study entry remain uninvolved) AND
 - No component with PD
- **Minor Response (MR):**
 - PR or CR in ≥ 1 component AND
 - SD in ≥ 1 component AND
 - No component with PD
- **Stable disease (SD):**
 - SD in ≥ 1 component AND
 - No better than SD or NI (site not involved at study entry and remains uninvolved) AND
 - No component with PD
- **Progressive Disease (PD):** Any component with PD

The overall response based on the combined evaluations is summarized in the table below. The best response observed at any time point for each individual patient will be considered that patient's best overall response on this study.

Primary tumor	Soft tissue or bone metastatic disease	Bone marrow metastatic disease	Overall response
CR	CR	CR	CR
CR for one category and CR or NI for remaining categories			CR
CR	CR	MD	PR
CR	PR	CR	PR
CR	PR	MD	PR
CR	PR	NI	PR
CR	NI	MD	PR
PR	CR	CR	PR
PR	CR	NI	PR
PR	CR	MD	PR

Primary tumor	Soft tissue or bone metastatic disease	Bone marrow metastatic disease	Overall response
PR	PR	CR	PR
PR	PR	NI	PR
PR	PR	MD	PR
PR	NI	CR	PR
PR	NI	NI	PR
PR	NI	MD	PR
NI	CR	MD	PR
NI	PR	CR	PR
NI	PR	MD	PR
CR	CR	SD	MR
CR	PR	SD	MR
CR	SD	CR	MR
CR	SD	MD	MR
CR	SD	SD	MR
CR	SD	NI	MR
CR	NI	SD	MR
PR	CR	SD	MR
PR	PR	SD	MR
PR	SD	CR	MR
PR	SD	MD	MR
PR	SD	SD	MR
PR	SD	NI	MR
PR	NI	SD	MR
SD	CR	CR	MR
SD	CR	MD	MR
SD	CR	SD	MR
SD	CR	NI	MR
SD	PR	CR	MR
SD	PR	MD	MR
SD	PR	SD	MR
SD	PR	NI	MR
SD	SD	CR	MR
SD	NI	CR	MR
NI	CR	SD	MR
NI	PR	SD	MR
NI	SD	CR	MR
SD	SD	MD	SD
NI	SD	MD	SD
SD	NI	MD	SD
NI	NI	MD	SD
SD	SD	SD	SD

Primary tumor	Soft tissue or bone metastatic disease	Bone marrow metastatic disease	Overall response
SD	NI	SD	SD
NI	SD	SD	SD
NI	SD	NI	SD
NI	NI	SD	SD
PD in any single category			PD
Response that is not evaluable for any single category that had measurable or evaluable tumor at baseline and no PD for any category			Not evaluable
Response evaluation not done for one or more category			Not done

Abbreviations: CR = complete response; MD = minimal disease; MR = minor response; NI = not involved (site not involved at baseline and remains not involved); PD = progressive disease; PR = partial response; SD = stable disease.

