Tumor evaluation: CT or MRI		End of Cycles 2, 4, and 6, then at the end every 4th cycle	
 Up to 1 week prior to the start of the next planned cycle of therapy Repeat assessment ≥4 weeks after initial response for patients with complete response, partial response, and minor response Use same modality throughout the study Scans will be performed and reviewed locally
Tumor evaluation: MIBG or PET CT		End of Cycles 2, 4, and 6, then at the end every 4th cycle	
 Up to 1 week prior to the start of the next planned cycle of therapy PET CT only for patients with non-MIBG avid lesions Repeat assessment ≥4 weeks after initial response for patients with complete response, partial response, and minor response Scans will be performed and reviewed locally
Bilateral bone marrow aspirates/biopsies		End of Cycles 2, 4, 6 and then after every 4th cycle - only for patients with marrow disease and all patients (even if no marrow disease) following Cycle 6	Up to 1 week prior to the start of the next planned cycle of therapy
Biomarkers – plasma	X	X	
 Collect pre-dose at C1D1 on participants CCI only Collect at disease progression and/or study discontinuation on participants CCI
Biomarkers - whole blood	X		
 For participants CCI whole blood dried blood spot For participants CCI whole blood sample If not collected during screening/baseline, then obtain at C1D1 If blood volume restrictions prevent collection during screening/baseline and C1D1, then sample can be collected at a subsequent timepoint

Part C			
Procedures	During Cycle 1	Cycle 2 onward	Instructions
			
 Only one sample is needed per patient See Section 8.8
Drug product acceptability and palatability questionnaire	Days 1 and 15	Cycle 2 Day 1 only	
 For patients \leq5 years old, only the caregiver will complete For patients \geq6 to $<$12 years old, patient and caregiver will complete For patients \geq12 years old, only the patient will complete Perform at time of dosing or within approximately 30 minutes after dose If method of abemaciclib administration or formulation (tablets to granules or vice versa) changes, the appropriate questionnaire corresponding to the new administration method and formulation should be completed at the clinic visit following this change

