Part A will be executed first to confirm the MTD of abemaciclib in combination with irinotecan and temozolomide. The MTD is defined as the highest dose level at which less than 33% of patients experience a DLT during Cycle 1. After the MTD of abemaciclib in Part A has been determined, Parts B and C will open. As Part B reduces cumulative exposure to myelosuppressive agents, it will enroll at a starting dose one level higher than the abemaciclib MTD in Part A (not to exceed 115 mg/m 2). Since Part B will not start at the lowest dose level (unless the lowest dose level of Part A is not tolerated), this sequential design has potential to minimize the number of patients necessary to complete Part B. The dose escalation/de-escalation method for abemaciclib in Parts A and B is described in detail in Section 4.1.1. Part C will utilize the MTD for the combination of abemaciclib, irinotecan, and temozolomide identified in Part A and the standard dosing of dinutuximab and GM-CSF (Mody et al. 2020) as the starting dose. Part C consists of two stages that will evaluate (1) safety and tolerability and (2) anti-tumor activity of the combination (details in Section 4.1.2).

Dose-limiting toxicities will be evaluated during the 21 days of treatment in Cycle 1. After the MTD has been identified, an expansion cohort for each part will be enrolled to further inform safety and PK and to confirm the tolerability in additional patients.

The cycle length is 21 days. Patients will continue study treatment until at least one of the discontinuation criteria is met (Section 7). Continuation on chemotherapy beyond Cycle 12 will be up to the investigator's discretion and the individual patient's situation. Prior to continuing the patient on chemotherapy beyond Cycle 12, the investigator should discuss with the Lilly clinical research physician/clinical research scientist (CRP/CRS).

The primary objective in Parts A and B is to determine the RP2D of abemaciclib in combination with irinotecan and temozolomide (Part A), and abemaciclib in combination with temozolomide (Part B) in patients with relapsed/refractory solid tumors. The secondary objectives include the assessment of the safety profile, preliminary anti-tumor activity, and abemaciclib acceptability and palatability. **CCI**

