In Part C only, patients will undergo a ¹²³I-MIBG scan for the presence or absence of MIBG avid lesions at the start of therapy and according to the SoA (Section 1.3.2). Those with MIBG avid lesions will be evaluable for MIBG response. For all patients with MIBG-avid lesions, including those with disease also detectable by CT/MRI, serial MIBG evaluations are required per the SoA. PET-CT may replace MIBG only for patients without MIBG avid lesions.

In Part C only, response confirmation is required based on a repeat assessment completed at least 4 weeks after initial response for patients with complete response, partial response, and minor response.

See Section 9.4.6 for definitions of the efficacy endpoints.

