### 7.3.1. *Primary Efficacy Endpoints*

The study was not designed to make an efficacy assessment in Parts A and B, while ORR will be assessed as co-primary endpoint in Part C if a RP2D is achieved. In Part C, ORR is the percentage of patients with a BOR  $\geq$  PR (CR, PR, and MR) per INRC (Park et al. 2017). The response criteria integrate the responses of all lesions using computed tomography/magnetic resonance imaging and/or MIBG/fluorodeoxyglucose-positron emission tomography lesions, and assessment of bone marrow disease. Details are provided in Protocol Section 9.4.6.2.1. All time point responses observed while on study treatment and during short-term follow-up, but before the initiation of post-discontinuation therapy, will be included in the derivation. The primary analysis of response will be based on confirmed responses as defined in [Table JPCS.7.2](#). However, summaries including unconfirmed responses will also be provided. For the interim analysis for Part C, unconfirmed responses may be used.

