**Table JPCS.7.2. Best Overall Response When Confirmation of Responses Required for Part C**

Overall Response First Time Point (1)	Overall Response Subsequent Time Period	Confirmed Best Overall Response
CR	CR ( $\geq$ 28 days from 1)	CR
CR	CR (<28 days from 1)	SD
CR	PR	SD
CR	MR	SD
PR	$\geq$ PR ( $\geq$ 28 days from 1)	PR
PR	$\geq$ PR (<28 days from 1)	SD
PR	MR	SD
MR	$\geq$ MR ( $\geq$ 28 days from 1)	MR
MR	$\geq$ MR (<28 days from 1)	SD
CR/PR/MR	SD	SD
CR/PR/MR	PD	SD if minimum duration of stable disease is met a , otherwise PD

Overall Response First Time Point (I)	Overall Response Subsequent Time Period	Confirmed Best Overall Response
CR/PR/MR	NE/Missing	SD if minimum duration of stable disease is met a , otherwise NE

Abbreviations: CR = complete response; MR = minor response; NE = not evaluable; PD = progressive disease; PR = partial response; SD = stable disease.

a CR/PR/MR occurs at study day >35.

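### Part C primary ORR: the 6-cycle analysis date falls 3-4 weeks before a first response at Cycle 6 can be confirmed, so a few late enrollees may be scored SD

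*Protocol*

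**What the plan says.** Protocol 9.4.6.2 fixes the time of the primary Part C analysis ("The primary analysis of ORR will occur 6 cycles after last patient has entered treatment") and gives the reason: "in order to ensure adequate response and durability of response data is available at the time of analysis". Protocol 4.1 states: "The cycle length is 21 days".

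The Part C schedule (Protocol 1.3.2) places tumor evaluations at "End of Cycles 2, 4, and 6, then at the end every 4th cycle", each allowed "Up to 1 week prior to the start of the next planned cycle of therapy". It also asks for a repeat assessment 4 weeks or more after an initial CR, PR or MR. Protocol 8.1 makes this a requirement for Part C: "response confirmation is required based on a repeat assessment completed at least 4 weeks after initial response".

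SAP 7.3.1 ties the primary endpoint to that requirement: "The primary analysis of response will be based on confirmed responses as defined in" Table JPCS.7.2. In that table, a first CR, PR or MR followed by a missing or non-evaluable assessment becomes "SD if minimum duration of stable disease is met", and NE otherwise. The footnote sets the minimum duration as a response after study day 35. Unconfirmed responses enter only the supplementary summaries and, optionally, the interim analysis. The SAP gives no data cut-off for the primary ORR analysis and no rule for a response whose confirmation is still pending.

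**The concern.** The analysis date and the date of the last early scan nearly coincide, while the endpoint needs a further 4 weeks after that scan. A genuine response first seen at the end of Cycle 6 in one of the last patients enrolled has no chance of being confirmed in time. The plan does not leave it as pending; the table turns it into SD.

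The final Part C decision (Protocol 4.1.2, Stage 2) is a count of responders against a threshold. A rule that can only remove responders, never add them, pushes that count one way. If the count is at the boundary, one patient decides the result.

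**Working it through.** **Inputs from the documents.** Cycle length 21 days (Protocol 4.1). Analysis 6 cycles after the last patient starts (9.4.6.2). Scans at the end of Cycles 2, 4 and 6, up to 7 days early (1.3.2). Confirmation at least 28 days after first response (8.1; SAP Table JPCS.7.2). 46 patients at the RP2D (SAP 6.3).

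**Timing.** Days are counted from first dose.

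- Analysis date = 6 × 21 = 126.
- Scan at end of Cycle k = 21k − (0 to 7).
- Earliest confirmation = scan day + 28.

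| First response at | Scan day | Earliest confirmation | Relative to day 126 |
|---|---|---|---|
| Cycle 2 | 35-42 | 63-70 | 56-63 days before |
| Cycle 4 | 77-84 | 105-112 | 14-21 days before |
| Cycle 6 | 119-126 | 147-154 | 21-28 days after |

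Only the Cycle 6 row fails, by 3-4 weeks.

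**Who is affected.** A patient who started d days before the last patient has 126 + d days of follow-up at the analysis. Confirming a Cycle 6 response needs 147-154 days, so the patient is affected when d is below 21 (scan 7 days early) to 28 (scan at cycle end). A cycle delay in that patient's own treatment widens the window: with 14 days of delay it becomes 35-42 days.

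**How it is scored.** A Cycle 6 scan is on study day 120-127, well past day 35. If the absent confirmation is handled under the missing row of Table JPCS.7.2, the score is always SD.

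**Effect on ORR.** Each such patient lowers the estimate by 1/46 = 2.2 percentage points.

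**Effect on power (illustration; all inputs assumed).** The plan's own figure of 46 cannot be checked directly, because the null and alternative ORR are redacted. At one-sided 0.025 and 80% power, one pair that reproduces it under Simon's optimal design is 42% versus 65%: stop if 5 or fewer of 11 respond; insufficient activity if 25 or fewer of 46 respond. Its exact type I error is 0.0246 and its power 80.2%.

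Suppose L late patients, all in Stage 2, have confirmed-response probability 0.65 × (1 − e), where e is the share of responders who first respond at Cycle 6. Expected lost responders = L × e × 0.65.

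| L | e | Expected lost | Power |
|---|---|---|---|
| 0 | – | 0 | 80.2% |
| 2 | 5% | 0.07 | 80.0% |
| 2 | 10% | 0.13 | 79.7% |
| 3 | 10% | 0.20 | 79.5% |
| 5 | 20% | 0.65 | 77.7% |

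A second pair that also gives 46, 40% versus 63% (7/15, 24/46), goes from 80.8% to 78.6-80.6% over the same range of L and e. Under the null the same substitution lowers the rejection probability, so type I error is not inflated.

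**The case against.** The strongest reply is that six cycles is a reasonable landmark: every on-schedule response at Cycle 2 or 4 has had its scheduled confirming scan by then, and Cycle 6 responses are also confirmed in patients who enrolled more than 4 weeks before the last one. This stands. A reader might infer that late-enrolled responders in general are lost, or that the stated aim of adequate response and durability data fails altogether. The documents support neither. The gap needs late enrolment (or a delay) together with a first response at Cycle 6.

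It can also be said that Protocol 9.4.6.2 gives no day count and no cut-off date, and that six cycles could mean the last patient's own six cycles. That patient's delays would then move the date too. The 3-4 week gap for an on-schedule patient remains under either reading.

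The unconfirmed-response summaries in SAP 7.3.1 would make an affected patient visible, and the repeat scan is already required, so the data would still be collected. Neither changes the formal count.

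Finally, Protocol 9.4.6.2.1 takes each patient's best response over all time points, with no mention of confirmation. Under that sentence the response would count. The explicit requirements in Protocol 8.1 and SAP 7.3.1 point the other way and most plausibly govern, but the texts do conflict.

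**Conclusion.** The concern holds as a small, one-directional loss. The 3-4 week gap follows from the documents alone. The SD score rests on reading a pending confirmation as missing in Table JPCS.7.2, and the gap has consequences only if the analysis date is also the data cut-off; nothing in either document says otherwise.

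The size is uncertain, because accrual rate and the share of first responses at Cycle 6 are not given and the design rates are redacted. Under the assumed ranges, fewer than one responder is lost on average (0.07 to 0.65 of 46) and power drops by 0.2 to 2.5 points. The conclusion would change only if the count fell at the threshold.

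Two stronger readings should be set aside. A reader might expect some of these patients to be scored NE; that cannot happen, since a Cycle 6 response always falls after study day 35. A reader might also see a threat to the validity of a positive result; the bias is conservative, so there is none. This is a low-cost improvement, not a flaw in the design.

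**What to change.** In Protocol 9.4.6.2 and SAP 7.3.1, define the primary ORR data cut-off as the date when every patient with a first CR, PR or MR at or before the end-of-Cycle-6 assessment has either had the required repeat assessment (at least 28 days later) or has progressed, started new anticancer therapy, died or left the study. For an on-schedule last patient scanned at the end of Cycle 6 and responding there, this is at least 126 + 28 = 154 days after first dose.

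Tie the date to the repeat assessments, not to a fixed allowance such as 28 days plus the 7-day scan window. The repeat assessment has a minimum interval but no latest date, so a fixed allowance would not guarantee confirmation.

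Also reconcile the best-response sentence in Protocol 9.4.6.2.1 with the confirmation requirement in Protocol 8.1 and SAP 7.3.1.

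The cost is a few sentences and a primary analysis about 4-5 weeks later. No visit or scan is added, since the repeat assessment is already required.
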